#### 4.5.3 Additional Safety Assessments

#### 4.5.3.1 Laboratory Data

Continuous laboratory parameter values measured at screening will be summarized using arithmetic mean, standard deviation, median, minimum, and maximum and the number of measurements.

Results from the urine hCG (and serum, if applicable) pregnancy test (as needed for women with childbearing potential) will be listed.

#### 4.5.3.2 Vital Signs

Vital sign values including the change from baseline will be summarized by visit using arithmetic mean, standard deviation, median, minimum, and maximum and the number of measurements.

The number and percentage of participants will be categorized by their maximum post-baseline SBP and DBP. A summary of postbaseline hypotension criteria will be given.

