29 NOV 2023

1.3 Schedule of Activities (SoA)

Visit Number	Screening	V1	V2 ^b	UNS c	Notes
Study Day, Window	D -14	D1	D14		
Window (Days)	-4 ^a		+4		
Informed consent	X				
Inclusion and exclusion criteria	Х	Х			Recheck clinical status before assignment and/or 1st dose of study intervention.
Demography	X				
Full physical examination including height and weight	X				
Optional: local lab- clinical chemistry, hematology	x				eGFR, albumin, hemoglobin, total bilirubin, ALT and AST values must be available at screening. Values obtained as part of routine management should be used if measured within 30 days prior to Visit 1. If data is unavailable, values should be determined using a local lab.
Serum OR urine pregnancy test (WOCBP only)		Х			If a urine test cannot be confirmed as negative (e.g., an ambiguous result), a serum pregnancy test is required.
Medical history	X				Includes substance usage and family history of premature CV disease
Current status of heart failure medical conditions		Х	Х		Collect any changes to heart failure medical condition (hospitalization, worsening of condition).
Prior and current medications	Х	Х	Х	Х	Assess at any visit including daily dose, time of intake and dosing regimen
Local 12-lead ECG	X				
Vital signs	X	Χ	X	X	Vital signs should be measured before study intervention intake. See Section 8.3.2.
Study Intervention Assignment		Χ			
Intake of Study Intervention		X			Study intervention should be taken orally with food at the same time each day, preferably in the morning. Date and time of study intervention intake will be recorded at Visit 1. Participants must remain at the site for 2 h after intake of first dose of study intervention. Study intervention is self-administered between Visit 1 and Visit 2. See Section 6 for additional details.
Study Intervention Accountability			Х	Х	
AE review		X	х	Х	See Section 8.4.Includes AESI. At Visit 1, the AE review should be conducted before and 2h after dosing. If AE review is suggestive of symptomatic hypotension, date, time, and severity will be recorded and vital signs should be re-assessed post dose.

AE = adverse event, AESI = adverse event of special interest, ALT = alanine transaminase, AST = aspartate aminotransferase, CV = cardiovascular, D = day, ECG = electrocardiogram, UNS = unscheduled, V = visit, WOCBP = women of child-bearing potential

a Screening must be completed 14-18 days before Visit 1.

b Visit 2 is the end of intervention visit.

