In clinical practice, titration of HF medications, including vericiguat, is often compromised by limited follow-up opportunities and complexity of care at each follow-up visit. This results in under treatment of HFrEF patients due to failure to achieve the maximum efficacious dose for treatments with established benefit. Achieving the target dose of HF treatments in a safe and fast manner remains a large unmet medical need in HFrEF patients. Keeping drug initiation/titration regimens as simple and as safe as possible is critical to HFrEF patients in order to achieve optimal doses of GDMT.

Currently, initiation of vericiguat starts with 2.5 mg, increasing to 5 mg at 2 weeks, then 10 mg at 4 weeks. Removing the 2.5 mg step has the benefit of patients starting on a more efficacious dose and achieving maximal (target) dose with a single titration.

This SAP is based on the clinical study protocol version 1.0 (dated 29 NOV 2023). The SAP describes the final analysis of the study. No statistical interim analysis will be performed. Table, figure and listing specifications are contained in a separate document. There are no changes to the analyses described in the protocol.

Version 1.0 Page: 7 of 15

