## 4. Statistical Analyses

#### 4.1 General Considerations

The statistical evaluation will be performed by using the software SAS (release 9.4 or higher; SAS Institute Inc., Cary, NC, USA).

All analyses will be performed on the SAF.

In general, continuous data will be summarized using the number of participants, mean, standard deviation, minimum, median, and maximum. For categorical data frequency tables will be provided. Summary statistics and frequency tables will be presented for Vericiguat, i.e. overall, and by visit (if applicable).

All data will be presented in the participant data listing as they are recorded on the eCRF, i.e., partially missing data will appear as such. Imputation of missing data is not planned.

Listings will be provided sorted by participant identifier.

Version 1.0 Page: 9 of 15

Data from unscheduled measurements will be listed, but not included in summary statistics or frequency tables.

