## 4.1.2 Repeated Measurements

If more than one measurement is available at screening, the last observation of those will be used for descriptive statistics tables as well as for frequency tables. In case of multiple measurements at planned time points after intake of study intervention, the earliest measured value will be used for descriptive statistics tables as well as for frequency tables.

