#### 4.5.2 Adverse Events

All AEs will be summarized using the Medical Dictionary for Regulatory Activities (the current version at the time of analysis) PTs grouped by SOC.

Any medical occurrences/conditions that begin in the period between signing the informed consent form and the start of study intervention, and which are not related to a protocol-required study procedure, will be recorded as medical history/current medical conditions, not as AEs.

Any AEs related to study procedures recorded after signing of informed consent but prior to first treatment with study intervention will be considered as pre-treatment AEs.

AEs are considered to be treatment-emergent if they started or worsened after first administration of study intervention until completion of study for the respective participant. Therewith pre-treatment AEs and non-treatment-emergent AEs are equivalent and there are no post-treatment AEs defined in this study.

Symptomatic hypotension as assessed by the investigator is considered an adverse event of special interest in this study.

Individual listings of all AEs will be provided including AE onset and end date relative to start and end date of intervention and the duration of the AE. Listings of treatment-emergent as well as non-treatment emergent serious AEs, AEs with fatal outcome and deaths not attributed to AEs as well as AEs resulting in discontinuation will be provided in addition.

Overall summaries of the number of participants with any AEs, pre-treatment AEs, TEAEs and treatment-emergent AESIs, treatment-emergent AESIs restricted to moderate and severe intensity and deaths together with AEs with fatal outcome will be generated.

The number of participants with serious AEs, TEAEs, intervention related TEAEs TEAEs leading to discontinuation of study intervention, intervention-related TEAEs leading to discontinuation of study intervention, TEAEs by maximum intensity, intervention-related TEAEs by maximum intensity, non-serious TEAEs, serious TEAEs, intervention-related serious TEAEs, deaths together with AEs with fatal outcome and TEAEs with fatal outcome will be summarized using PTs grouped by SOC. Treatment-emergent AESIs and treatment-emergent AESIs restricted to moderate and severe intensity will be summarized using PTs.

An overview of TEAEs and serious TEAEs by demographic subgroups will be provided.

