#### **Subgroup Analyses**

The following subgroups as defined in the CSP will be regarded:

- Participants with recent worsening HF event (group 1)
- Participants without recent worsening HF event (group 2)
- Participants receiving an ARNI, total and in group 1/2, respectively.
- Participants receiving an ARNI and no SGLT2 inhibitor, total and in group 1/2.
- Participants receiving a SGLT2 inhibitor, total and in group 1/2, respectively.
- Participants receiving an SGLT2 inhibitor and no ARNI, total and in group 1/2.
- Participants receiving both, an ARNI and a SGLT2 inhibitor, total and in group 1/2, respectively (only for vital signs and AESIs and only if >10% of all participants).
- Participants receiving neither an ARNI nor a SGLT2 inhibitor, total and in group 1/2, respectively (only for vital signs and AESIs and only if >10% of all participants).

The occurrence of all above defined subgroups will be summarized in the demographics section.

Version 1.0 Page: 14 of 15

All ratios specified in Table 4-1 will be regarded restricted to the above specified subgroups as well.

Additionally, tables summarizing heart rate and blood pressure measurements will be shown for the above defined subgroups as well to account for changes in vital signs in the particular groups.

Also, tables summarizing AESIs, if occurred, will be shown for the subgroups listed above.

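### The SAP categorises participants by maximum post-baseline blood pressure and keeps unscheduled readings out of tables, so the category table can miss low readings that sites collect

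*SAP*

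**What the plan says.** SAP 4.5.3.2 plans three blood-pressure outputs: by-visit summaries (including the minimum and the change from baseline), a category table, and a summary of hypotension criteria. For the category table it says: "The number and percentage of participants will be categorized by their maximum post-baseline SBP and DBP". The hypotension summary is promised in one sentence, with no criteria, thresholds or data scope.

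Two general rules decide which readings enter tables. SAP 4.1: "Data from unscheduled measurements will be listed, but not included in summary statistics or frequency tables". SAP 4.1.2, for several measurements at a planned time point after intake: "the earliest measured value will be used for descriptive statistics tables as well as for frequency tables". Neither rule has an exception for blood pressure. SAP 1 notes: "Table, figure and listing specifications are contained in a separate document".

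The protocol's Schedule of Activities fixes the timing of readings: "Vital signs should be measured before study intervention intake". At Visit 1 there is a conditional extra reading: "If AE review is suggestive of symptomatic hypotension, date, time, and severity will be recorded and vital signs should be re-assessed post dose". Footnote c of the schedule makes vital signs mandatory at unscheduled visits for adverse-event review.

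Hypotension is also reported in other ways. SAP 4.5.2: "Treatment-emergent AESIs and treatment-emergent AESIs restricted to moderate and severe intensity will be summarized using PTs". The SAP's subgroup section adds: "Additionally, tables summarizing heart rate and blood pressure measurements will be shown for the above defined subgroups as well". It also repeats the tables of adverse events of special interest (AESI) by subgroup.

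**The concern.** Protocol 4.3 predicts a total fall in systolic pressure (SBP) of 4.0 to 5.0 mmHg with the 5 mg start. Protocol 4.2 centres monitoring on continuation of study intervention and on symptomatic hypotension, which is also the AESI (Protocol 8.4.6). A per-participant maximum looks in the opposite direction. In addition, the readings closest to an event are collected outside the schedule, and SAP 4.1 removes those from every table.

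What is exposed is the measured blood pressure, not the count of symptomatic events. The AESI covers symptomatic hypotension only. Unless the table specifications make an exception, an asymptomatic low reading at an unscheduled visit reaches no table, except where the investigator judges it clinically significant and reports it as an adverse event. For symptomatic participants, the category table and any subgroup version of it (ARNI, SGLT2 inhibitor, group 1 or 2) can look benign beside the AESI count. Protocol 8.3.2 itself calls accurate blood-pressure measurement essential for assessing tolerability and detecting safety signals.

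**Working it through.** The plan states no figure for this point, so there is none to reproduce. The check has three steps.

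**1. Which readings can enter the category table**

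- Visit 1 before intake is the baseline (SAP 4.1.1), so it is not post-baseline.
- Visit 2, before that day's intake, is the only routine scheduled post-baseline reading (Protocol 1.3). Protocol 7.1 requires participants with moderate to severe symptomatic hypotension to stop drug and keeps them in the study to Visit 2. Their value is off drug; others may still be on drug.
- Unscheduled visits are excluded by SAP 4.1.
- The SAP does not say whether the symptom-triggered Visit 1 post-dose re-assessment counts as scheduled. If it counts as a planned time point and is repeated, SAP 4.1.2 keeps the earliest value, not the lowest.

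The table therefore draws on Visit 2 alone or, at most, on Visit 2 plus a Visit 1 re-assessment.

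**2. Statistic against data scope**

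The readings are assumed (SBP, mmHg). Case A: unscheduled Day 3 = 84, Visit 2 = 114, no Visit 1 re-assessment. Case B: the same, plus a Visit 1 post-dose reading of 88 that counts as scheduled.

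| Rule | Case A | Case B |
|---|---|---|
| As written: maximum, scheduled only | max{114} = 114 | max{88, 114} = 114 |
| (a) minimum, scheduled only | min{114} = 114 | min{88, 114} = 88 |
| (b) maximum, all post-intake readings | max{84, 114} = 114 | max{88, 84, 114} = 114 |
| (a) and (b): minimum, all post-intake readings | min{84, 114} = 84 | min{88, 84, 114} = 84 |

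In Case A there is one eligible value, so maximum equals minimum and the exclusion rule alone loses the low reading. In Case B the maximum selects the higher of two eligible values. Only the two changes together return the lowest reading in both cases.

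The same pattern appears in counts. Assume that 2, 5 or 10 of 100 participants have one low extra reading and a recovered Visit 2 value. The table then counts 0 low participants under each of the first three rules, and 2, 5 or 10 under the fourth.

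**3. Scale**

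The nearest figure in the documents is VICTORIA's 14-day rate of symptomatic hypotension or syncope with a 2.5 mg start: 2.0% on vericiguat and 1.2% on placebo (Protocol 2.2). With n = 100 (Protocol 9.5, SAP 5), the expected count is 100p and P(at least one) = 1 − (1 − p)^100.

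| p | Expected count | P(at least one) | 95% binomial range |
|---|---|---|---|
| 1.2% | 1.2 | 0.701 | 0 to 4 |
| 2.0% | 2.0 | 0.867 | 0 to 5 |
| 4.0% (assumed) | 4.0 | 0.983 | 1 to 8 |

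These are counts of symptomatic events. Not every such participant would have an unscheduled reading, and asymptomatic low readings are not in the rate. The table shows the order of magnitude and does not estimate lost readings.

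**The case against.** The strongest reply is that SAP 4.5.3.2 has two consecutive outputs: the maximum categories may describe the high side, and the hypotension summary the low side. On that reading, replacing maximum by minimum removes one table and may duplicate the other. Further, with a single eligible reading the word maximum changes nothing, so the operative rule is SAP 4.1. The table specifications are in a document not available here and could define the criteria and admit unscheduled readings. Symptomatic hypotension is already covered by the primary endpoint (when moderate to severe) and by the AESI tables, and all unscheduled readings are listed. Finally, scheduled-only tables are a defensible choice, because symptom-triggered readings give some participants more chances of a low value.

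Part of this stands. Changing the statistic alone would alter almost nothing, the frequency of lost readings is unknown, and the scheduled-only rule suits the by-visit summaries.

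The rest does not remove the defect. The hypotension summary has no stated data scope, so the SAP 4.1 exclusion applies to it by default. Neither document raises high blood pressure as a hazard of treatment, and if the largest decrease was meant, the text does not say so. An exception that exists only in the table specifications would conflict with the SAP's general rule. An AESI count does not report measured pressure, and the by-visit minimum is one group value at Visit 2, not a count of participants with low readings.

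**Conclusion.** The concern holds. Followed as written, the maximum rule and the unscheduled-data rule together keep low readings that the protocol requires sites to collect out of the category table and, by default, out of the hypotension summary. This should be fixed, as a secondary safety-reporting defect. The primary endpoint has no blood-pressure threshold and does not change, no hypothesis test is involved, and the readings remain in listings.

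The wording of the two rules is certain. The amount of information lost is not: the blood pressures in the illustration are assumed, and the event rates come from symptomatic events at a lower starting dose. The conclusion also assumes that the separate table specifications contain no exception.

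**What to change.** Make both changes together.

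- (a) In SAP 4.5.3.2, categorise participants by minimum, not maximum, post-baseline SBP and DBP.
- (b) For the minimum-pressure and hypotension-criteria tables, including any subgroup versions, use every reading after first intake. Name unscheduled visits and Visit 1 post-dose re-assessments, and write this as an explicit exception to SAP 4.1 and 4.1.2.

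Keep the scheduled-only rule for the by-visit summaries. Add a table footnote that unscheduled readings are symptom-triggered, so participants with more visits have more chances of a low value.

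The cost is SAP wording, table-shell changes and one footnote; no new data and no protocol amendment are needed. The downside is unequal numbers of readings per participant. If each reading had an assumed, independent 3% chance of being low, one reading gives 3%, while three give 1 − (1 − 0.03)^3 = 0.087, or about 9%. The footnote discloses this.

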# 4.5.3.3 Electrocardiogram

Electrocardiogram values measured at screening will be summarized using arithmetic mean, standard deviation, median, minimum, and maximum and the number of measurements.

# 4.6 Other Analyses

#### 4.6.1 Other Variables and/or Parameters

Not applicable.

#### **Subgroup Analyses**

The following subgroups as defined in the CSP will be regarded:

- Participants with recent worsening HF event (group 1)
- Participants without recent worsening HF event (group 2)
- Participants receiving an ARNI, total and in group 1/2, respectively.
- Participants receiving an ARNI and no SGLT2 inhibitor, total and in group 1/2.
- Participants receiving a SGLT2 inhibitor, total and in group 1/2, respectively.
- Participants receiving an SGLT2 inhibitor and no ARNI, total and in group 1/2.
- Participants receiving both, an ARNI and a SGLT2 inhibitor, total and in group 1/2, respectively (only for vital signs and AESIs and only if >10% of all participants).
- Participants receiving neither an ARNI nor a SGLT2 inhibitor, total and in group 1/2, respectively (only for vital signs and AESIs and only if >10% of all participants).

The occurrence of all above defined subgroups will be summarized in the demographics section.

Version 1.0 Page: 14 of 15

All ratios specified in Table 4-1 will be regarded restricted to the above specified subgroups as well.

Additionally, tables summarizing heart rate and blood pressure measurements will be shown for the above defined subgroups as well to account for changes in vital signs in the particular groups.

Also, tables summarizing AESIs, if occurred, will be shown for the subgroups listed above.

# 4.7 Interim Analyses

No interim analysis is planned.

Due to the nature of this study, participant-level intervention assignment information is available during study conduct. However, manual interim calculations of tolerability rates will not be done in order to protect the integrity of the study.

# 4.8 Changes to Protocol-planned Analyses

Not applicable.

## 5. Sample Size Determination

Based on the evidence of a strong safety profile of vericiguat and the recommendation provided by FDA, the sample size of approximately 100 participants is considered appropriate to assess the tolerability of the 5 mg initiation dose for vericiguat.

# **6.** Supporting Documentation

# 6.1 Population characteristic

#### 6.1.1 Participant disposition

The number of participants enrolled, assigned to study intervention and valid for the SAF will be summarized for each study site.

The number of all participants as well as the number of sites will further be summarized by country/region.

The number of participants with important protocol deviations and the number of screen failures will be summarized overall and by country/region and study site.

The number of participants per important deviation category and validity finding will be presented.

A disposition summary will be presented summarizing the number of participants starting and completing the respective study phase, the number of participants discontinuing it and the primary reason for discontinuation. The number of participants completing the overall study will be provided in addition. Participants who completed the study are those who were followed for the duration of the study irrespective of discontinuation of study intervention.

#### 6.1.2 Demography and other baseline characteristics

All demographic and baseline characteristics will be summarized using descriptive statistics by intervention, i.e. overall.

Version 1.0 Page: 15 of 15

Demographic and baseline assessments to be summarized will include the following age groups:

< 18 years, 18-64 years, 65-84 years, >= 85 years and < 65 years, >= 65 years.

#### 6.1.3 Protocol deviations

The number of participants with important protocol deviations and the number of screen failures will be summarized by country. In addition, the important protocol deviations will be listed and summarized in a frequency table (based on all participants randomized).

## 6.1.4 Medical history

Medical history will be tabulated using medical dictionary for regulatory activities (current version at the time of analysis) terms. The number of participants with medical history findings will be presented by primary system organ class and preferred term.

#### 6.1.5 Prior and concomitant medication

For prior and concomitant medications, the following definitions apply:

- Prior medication: Medication taken before start of the study intervention intake, (regardless of when it ended).
- Concomitant medication: Medication taken after first study intervention intake (regardless of when it started or ended).

Prior and concomitant medication will be coded to ATC classification codes according to the World Health Organization Drug Dictionary (current version at the time of analysis). The number of participants taking prior and concomitant medication will be presented by study arm and overall using ATC classes and subclasses.

